6. STUDY PARTICIPANTS

7.1 Study Setting

The study will take place at Occuity's office in Reading.

7.2 Overall Description of Study Participants

Patients over the age of 18, with no active corneal pathology, ocular inflammatory condition, or recent eye surgery.

7.3 Eligibility Criteria

Inclusion Criteria

The participant must meet ALL the following criteria to be considered eligible for the study:

- Male or Female, aged 18 years or above.
- Participant is willing and able to give informed consent for participation in the study.
- Able and willing to comply with all study requirements.

Exclusion Criteria

The participant may not enter the study if ANY of the following apply:

- Any ocular surgery within 6 months

- Known active corneal abnormalities (e.g. Keratoconus, epithelial defects)
- Previous corrective refractive surgery (e.g. LASIK, PRK)
- Current ocular inflammatory or infectious disease (e.g. Uveitis, keratitis, corneal ulcers)
- Contact lens use within the last week
- Any contraindications to use of topical anaesthetic eye drops
- Any other pathology which the clinician or investigator believe may affect the accuracy of the CCT measurement

7. SAMPLING

To achieve a statistically significant result in this crossover, non-inferiority study, with the alpha error set at <0.025, and power at 0.95, and a non-inferiority limit of 2 μ m, 163 eyes will be required, which would likely mean 82 to 100 participants, assuming most are able and willing to have tests performed on both eyes. Calculations are based on the formula:

$n = f(\alpha, \beta) \times 2 \times \sigma^2 / d^2$ (where σ is the standard deviation).

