3. BACKGROUND AND RATIONALE

The cornea is a thin, transparent structure at the front of the eye; its surface, as well as the overlying tear film, is responsible for the majority of the eye's refractive power.

Accurate and precise measurement of corneal thickness is important in the diagnosis and management of many ocular diseases. In particular, the central corneal thickness (CCT) measurement is a key parameter to consider when planning for procedures such as refractive surgery, and in the diagnosis of glaucoma.

Refractive error is the leading cause of reversible visual impairment worldwide; it is therefore unsurprising corrective refractive surgery is one of the most widely performed procedures globally. In the United Kingdom, the most frequently performed refractive surgery are laser assisted surgical procedures, such as laser assisted in situ keratomileusis (LASIK), Laser epithelial keratomileusis (LASEK), and Photorefractive Keratectomy (PRK). All of these techniques involve ablating the cornea with a laser to achieve a specific shape. Having an accurate measurement of corneal thickness is therefore of utmost importance in the planning stages, as excessive ablation of the cornea can lead to corneal ectasia, a significant complication of refractive surgery.

Glaucoma is a progressive disease which causes irreversible vision loss, and with ever aging populations, it is now one of the leading causes of irreversible blindness worldwide. Although it is considered to be multifactorial in aetiology, with both genetic and acquired factors contributing to its development and progressions, it is still widely accepted that the intraocular pressure (IOP) is the only modifiable factor in its management to prevent or slow further visual loss. (5).

IOP measurement is typically done in hospital clinics using a Goldmann applanation tonometer. The pressure reading is affected by the corneal thickness – a thick cornea will give a falsely elevated IOP reading, which may result in a patient with healthy eyes being commenced on unnecessary treatment, while conversely a thin cornea may give a falsely low pressure reading, which can result in patients with glaucoma not being started on sight-saving treatment. It has been estimated that a 10% increase in CCT can result in an apparent IOP increase of 3.4mmHg (2).

Ultrasound Pachymeter

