4. AIMS AND OBJECTIVES

Primary Objective

To determine whether the Occuity PM1 device is non-inferior in measuring central corneal thickness when compared to ultrasound pachymetry, the Lenstar and the Pentacam.

Secondary Objective

The Investigation aims to assess long-term safety of the Occuity PM1 device when used under the conditions and for the purposes intended, to ensure it will not compromise the clinical condition or the safety of patients, or the safety and health of users or, where applicable, other persons.

If the evidence collected during this investigation is not sufficient to demonstrate that the PM1 Pachymeter does not perform under the conditions and for the purposes intended, it may be deemed possible that further investigation may be required. If it is deemed that further clinical investigation(s) are required, it is understood that a new MHRA application will be undertaken.

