6.2 Primary and Secondary Endpoints/Outcome Measures

The central corneal thickness measurements taken by the three devices: Occuity PM1, the ultrasound pachymeter and Lenstar. Demonstrating that the Occuity PM1 Pachymeter is not inferior to the LenStar in terms of equivalency to a 95% confidence level using the Bland Altmen equation/approach based on +/-20micron equivalency.

Occuity outlines the target range of the PM1 to be within 300-800um. This is because we have already tested this target range with known artefacts. However, the patient population which

is being evaluated will consist only of patients with no known corneal abnormalities, corrective refractive surgeries, ocular inflammatory conditions etc.

It is likely that ~95% of corneal thicknesses which are measured will be within the range of 480um to 620um, therefore ~5% will be outside of the expected range. However, despite there being no history of the pre-stated conditions, there is still the likelihood of this study being able to assess patients with thick/thin corneas as part of the scope, as this is the percentage population who naturally have very thin or very thick corneas.

Secondary Endpoint

If evidence is not sufficient to demonstrate that the PM1 Pachymeter does not perform outside of the target range, it is understood that further investigation may be required. If it is deemed that further clinical investigation(s) are required, it is understood that a new MHRA application will be undertaken.

SAFETY OUTCOMES MEASURES

The type and number of adverse events, serious adverse events and any other device issues will be recorded. Adverse events and devices issues not reflected on the product label will be reported to the manufacturer and, for the Occuity product, will be dispositioned according to the Sponsor's complaint handling procedures for post-market products.

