17.2 Analysis of Endpoints

On completion of data collection, the primary endpoint will be analysed using paired tests or non-parametric equivalents, to compare the CCT measurement achieved using the ultrasound pachymeter and the Occuity PM1 device, and then between the values obtained from the Lenstar, Pentacam and Occuity PM1 device. The level of statistical significance will be set at $p < 0.05$.

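### The objective and the 163-eye calculation are one-sided non-inferiority, the endpoint is two-sided equivalence, and the planned tests address neither; the stated 95% power covers only the one-sided claim

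*Protocol*

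**What the plan says.** Four parts of the protocol bear on what counts as success.

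- **Objective.** Section 4 sets out "To determine whether the Occuity PM1 device is non-inferior in measuring central corneal thickness when compared to ultrasound pachymetry, the Lenstar and the Pentacam". The Synopsis (Section 2) puts the research question and the objective in the same non-inferiority terms.
- **Sample size.** Section 7 describes a crossover "non-inferiority study, with the alpha error set at <0.025, and power at 0.95, and a non-inferiority limit of" 2 µm, the only limit it sets. The result is 163 eyes, expected from 82 to 100 participants. The formula is n = f(α, β) × 2 × σ² / d². No value of σ is given, and α is not labelled one- or two-sided.
- **Endpoint.** Section 6.2, repeated in the Synopsis, reads "Demonstrating that the Occuity PM1 Pachymeter is not inferior to the LenStar in terms of equivalency to a 95% confidence level". It names a Bland-Altman approach and a ±20 µm range.
- **Analysis.** Section 17.2 plans paired significance tests (or rank-based counterparts) of PM1 against the other devices, with "The level of statistical significance will be set at" p < 0.05.

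Section 3 explains why thickness matters: a thick cornea inflates the pressure reading and may lead to needless treatment, "while conversely a thin cornea may give a falsely low pressure reading", so that treatment may be missed.

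**The concern.** Non-inferiority suits an outcome with a good and a bad direction: one bound is tested and the other side is left free. A corneal thickness reading has no good direction, and the protocol does not say which side its non-inferiority limit guards. The endpoint's ± form asks for both sides to be excluded. The objective and the endpoint are therefore different claims and could give different answers on the same data.

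The planned analysis settles neither. A non-significant paired test does not show agreement, and a significant one may reflect a trivial bias. As written, a reader cannot tell which result would allow the sponsor to say that PM1 agrees with a comparator, or with what power the trial could show it.

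**Working it through.** **Inputs.** From Section 7: α = 0.025 (read as one-sided), power 0.95, d = 2 µm, n = 163 eyes and the formula above. From Section 6.2: ±20 µm and 95% confidence. Assumed, because the protocol gives no values: σ, a true difference of zero, and eyes treated as independent.

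**Step 1: reproduce 163.** f = (1.960 + 1.645)² = 12.995. The figure cannot be reproduced without σ. With σ = 5 µm, n = 12.995 × 2 × 25 / 4 = 162.4, rounded up to 163. Solving back from 163 gives σ = 5.01. For comparison, σ = 4 gives 104 eyes and σ = 6 gives 234. Had α = 0.025 been meant as two-sided, the back-solved σ would be 4.65. The factor f is that of a test of one bound.

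**Step 2: one-sided power at 163 eyes.** SE = 5 × √(2/163) = 0.554. Power = Φ(2/0.554 − 1.96) = Φ(1.651) = 0.951.

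**Step 3: two-sided equivalence at the same limit and the same α per side.** Power = 2Φ(d/SE − 1.96) − 1 = 2 × 0.9506 − 1 = 0.901 (0.898 with t quantiles). If the one-sided power is exactly 1 − β at zero true difference, equivalence power is 1 − 2β = 1 − 2 × 0.05 = 0.90. This does not depend on σ.

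**Step 4: eyes needed to keep 95% for that claim.** f = (1.960 + 1.960)² = 15.37, and 15.366 × 2 × 25 / 4 = 192.07, so 193 eyes at σ = 5.

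**Step 5: sensitivity of the 90%.**
- At 0.05 per side, equivalence power at 163 eyes is 95.1%.
- At a true difference of 0.5 µm (σ = 5, 0.025 per side), non-inferiority power is 77.3% and equivalence power 76.8%, so the gap nearly closes.

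**Step 6: the endpoint's own ±20 µm, at 163 eyes.**
- *Mean difference:* power is above 99.9% for σ from 5 to 20 µm, and 98.9% at σ = 40.
- *Limits of agreement with their 95% confidence intervals inside ±20 µm (simulated):* the result turns on the SD of the paired differences.

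| SD of differences (µm) | Power |
|---|---|
| 7.07 (= 5√2) | 99.99% |
| 8 | 94.7% |
| 9 | 32% |
| 10 | 1.4% |

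**The case against.** **The 90% is not the endpoint's power.** This is the strongest objection, and it stands. A reader might infer from Step 3 that the trial has only 90% power for its stated endpoint. The documents do not support that: the 90% uses Section 7's 2 µm, while Section 6.2 uses ±20 µm. On neither reading of Section 6.2 does 90% follow.

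**The planned range may already cover 193 eyes.** One hundred participants giving both eyes make 200. With σ = 5, SE = 5 × √(2/200) = 0.5 and equivalence power at ±2 µm is 2Φ(4 − 1.96) − 1, about 96%. This is fair, although the upper end of the range may allow for participants who contribute one eye. It limits the practical loss but does not settle which claim is tested.

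**The two significance levels need not conflict.** A reader might infer that 0.05 in Section 17.2 doubles the 0.025 in Section 7. It would do so only if 0.05 were applied one-sided, which the protocol never says. One-sided 0.025 matches two-sided 0.05 and the 95% confidence level in Section 6.2.

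**A badly biased device would not simply pass.** A reader might also infer that a device over-reading by, say, 30 µm would be declared successful on a lower-bound test. It would fail the ±20 µm criterion, so this needs Section 6.2 to be ignored. Section 3, moreover, describes how true thickness biases tonometry. It supports the view that neither direction is favourable, but it does not measure the harm from a pachymeter error.

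**Detail can be left to an analysis plan.** That is true of detail. The point here is that sections of the protocol contradict one another, which a separate plan does not remove.

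**Conclusion.** The contradiction is in the text and holds whichever limit is kept: a non-inferiority objective and sample size, a two-sided equivalence endpoint, and difference tests that decide neither. It needs correcting because it leaves the success criterion undefined.

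The power statement is narrower. Section 7's 95% is for a one-sided claim. For two-sided equivalence of the mean difference it falls to about 90%, given a ±2 µm limit, 0.025 per side, zero true difference and 163 eyes treated as independent. No power figure can be attached to Section 6.2 until it is clear whether ±20 µm applies to the mean difference or to the limits of agreement and, for the latter, what SD is assumed. The tenfold gap between 2 and 20 µm has to be resolved in the same revision; this review takes no position on which is right.

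**What to change.** 1. In Sections 2, 4, 6.2 and 7, replace 'non-inferior' and its variants with 'equivalent'.
2. State one decision rule, identically, in Sections 6.2, 7 and 17.2 (and in the Synopsis): PM1 is equivalent when the two-sided 95% confidence bounds lie inside both −L and +L. Give a single L, and say whether the bounds are for the mean difference or, in line with the Bland-Altman approach, for the limits of agreement. L and the quantity must be chosen together: with an SD of differences of 7.07 µm, the limits of agreement are already about ±13.9 µm (1.96 × 7.07) around the mean difference, so ±2 µm could not be met for them.
3. In Section 17.2, make this rule the primary analysis in place of the paired difference tests at p < 0.05.
4. In Section 7, restate the power for that rule with L and σ given. About 90% for 163 eyes is right only if L = 2 µm on the mean difference at 0.025 per side, with zero true difference and independent eyes.

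The cost is protocol wording. The restatement itself needs no more participants. Keeping 95% at L = 2 µm on the mean would take about 193 eyes at σ = 5, within the 200 that 100 participants could supply. If limits of agreement are chosen, the sample size has to be recalculated from a stated SD of differences and may change.

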2. SYNOPSIS

Study Title	Assessment of the Occuity PM1 pachymeter
Research question / hypothesis	Is the Occuity pachymeter non inferior in it's measurement of central corneal thickness compared to the ultrasound pachymeter, Lenstar and Pentacam.
Study Design	Research Study
Study Participants	Volunteers with no corneal pathology
Planned Sample Size	82-100 participants
Follow-up duration	N/A
Planned Study Period	1 month
Primary Objective	To determine whether the Occuity PM1 device is non-inferior in measuring central corneal thickness when compared to ultrasound pachymetry, the Lenstar and the Pentacam.
Secondary Objectives	The Investigation aims to assess long-term safety of the Occuity PM1 device when used under the conditions and for the purposes intended, to ensure it will not compromise the clinical condition or the safety of patients, or the safety and health of users or, where applicable, other persons.
Primary Endpoint	The central corneal thickness measurements taken by the three devices: Occuity PM1, the ultrasound pachymeter and Lenstar. Demonstrating that the Occuity PM1 Pachymeter is not inferior to the LenStar in terms of equivalency to a 95% confidence level using the Bland Altmen equation/approach based on +/-20micron equivalency.
Secondary Endpoints	If evidence is not sufficient to demonstrate that the PM1 Pachymeter does not perform outside of the target range, it is understood that further investigation may be required. If it is deemed that further clinical investigation(s) are required, it is understood that a new MHRA application will be undertaken.
Safety Outcomes	The type and number of adverse events, serious adverse events and any other device issues will be recorded. Adverse events and devices issues not reflected on the product label will be reported to the manufacturer and, for the Occuity product, will be dispositioned according to the Sponsor's complaint handling procedures for post-market products.
Intervention (s)	N/A

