The device has an intuitive touchscreen display interface, and a series of 9 LEDs which provides the illumination needed to align the device in front of the eye. Once alignment is achieved, the measurement can take place by pressing the start button on the touchscreen display. During preliminary testing at the parent company, it has been shown the alignment and measurement process takes less than 10 seconds in total, after which a reading will be shown on the digital display of the device. The device is reported to have high reliability (variation of approximately 10um with repeat readings of the same eye), and comparable results to the Lenstar LS900 Biometer during initial testing.

The LED light system consist of a partial ring of 9 white LEDs at a radius of 8.75mm and spaced at 30° intervals. The total power is 2.4 mWm⁻² which is will within the 10 mWm⁻² blue light hazard eye safety limit. The maximum power of the infrared beam is 50µW, which given the expected exposure time of less than 10 seconds, is considered Class 1 eye safe according to BS EN 60825.

Lenstar LS 900 (Haag-Streit AG, Koeniz, Switzerland)

The Lenstar is an optical device which utilises an 820nm super-luminescent diode and allows for high resolution measurements of the structures in the eye, including CCT. Its use is well established in the hospital clinic setting, and measurements do not require the use of anaesthetic drops or corneal touch. A drawback of this device is that it is large and heavy, and therefore not portable or as fast to use, unlike the ultrasound pachymeter or the Occuity PM1 device.

Pentacam (Oculus Optikgerate GmbH (Germany)

Very similar to the Lenstar, the Pentacam is an optical device which also utilises an 820nm super-luminescent diode and allows for high resolution measurements of the structures in the eye, including CCT. Its use is well established in the hospital clinic setting, and measurements do not require the use of anaesthetic drops or corneal touch. A drawback of

this device is that it is large and heavy, and therefore not portable or as fast to use, unlike the ultrasound pachymeter or the Occuity PM1 device.

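### The 95% power belongs to a 2 µm limit, the primary endpoint is judged at ±20 µm on an unnamed quantity, and Section 17.2 tests it with no margin

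*Protocol*

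**What the plan says.** Three places in the Protocol deal with the same primary question.

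- **Section 7 (Sampling)** sets the design "with the alpha error set at <0.025, and power at 0.95, and a non-inferiority limit of 2" µm and concludes that "163 eyes will be required, which would likely mean 82 to 100 participants". It gives the formula n = f(α, β) × 2 × σ² / d². It identifies σ as the standard deviation but gives no value or source, and does not say which standard deviation it is.
- **Section 6.2 and the Synopsis (Primary Endpoint)** require the PM1 to be shown "not inferior to the LenStar in terms of equivalency to a 95% confidence level using the Bland Altmen equation/approach based on +/-20micron equivalency". The sentence does not say whether ±20 µm bounds the mean difference, the 95% limits of agreement, or the outer confidence bounds of those limits. It uses non-inferiority and equivalence language together, so the direction is open too.
- **Section 17.2** states that "the primary endpoint will be analysed using paired tests or non-parametric equivalents", first against ultrasound and then against the Lenstar and Pentacam, at p < 0.05. It names no margin, confidence interval or limits of agreement.

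The comparator also varies. Section 4 names ultrasound, Lenstar and Pentacam; the ±20 µm criterion names the Lenstar alone; Section 17.2 starts with ultrasound. No section connects 2 µm with ±20 µm, or either of them with the paired tests.

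**The concern.** A study should have one success criterion, a power statement for that criterion, and an analysis that applies it. Here the power is attached to one limit, success to another ten times as wide, and the analysis to neither.

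This has two consequences. A reader who takes 95% as the chance of meeting the ±20 µm criterion is misinformed. And the verdict can depend on which section is followed. A non-significant paired test does not demonstrate agreement, and a significant one does not refute it: a clinically trivial bias can be significant while every reading of ±20 µm is met. If the choice is left open until the data are in, it can be made with the result in view.

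**Working it through.** **Inputs from the Protocol.** α < 0.025 (read as one-sided), power 0.95, d = 2 µm, 163 eyes and the formula (Section 7); ±20 µm (Section 6.2); p < 0.05 (Section 17.2). **Assumed, because not given:** σ, the SD of between-device differences, and the bias. Eyes are treated as independent unless stated otherwise.

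**1. Reproducing 163.** f = (1.960 + 1.645)² = 12.995.

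- σ = 5, d = 2: n = 12.995 × 2 × 25 / 4 = 162.4, rounded up to 163.
- σ = 50, d = 20: n = 12.995 × 2 × 2500 / 400 = 162.4, also 163.

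The formula depends only on σ/d = 2.5, so 163 is consistent with either limit. The Protocol supplies neither value of σ. Section 6.2 expects about 95% of corneas between 480 and 620 µm, which implies a between-eye SD near 140 / 3.92 = 36 µm. That would be the wrong kind of SD for a paired comparison, but it is of the same order as 50, so a dropped zero cannot be excluded.

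The kind of σ matters as well. If σ = 5 is a per-device SD with independent errors, the SD of differences is 5√2 = 7.07 µm. If it is already the SD of differences, the factor 2 is not needed and 12.995 × 25 / 4 = 81.2, or 82 eyes, would do at 2 µm.

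**2. Power of a ±20 µm criterion with 163 eyes and zero bias** (simulation, 1,000,000 draws of mean and SD). The rules are:

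- M: the 95% CI of the mean difference lies inside ±20.
- L: mean ± 1.96 SD lies inside ±20.
- O: L, widened by 1.96 × SD × √(1/n + 1.96²/(2(n−1))), lies inside ±20.

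| Assumed SD of differences (µm) | M | L | O |
|---|---|---|---|
| 7.07 | 100% | 100% | 100% |
| 8 | 100% | 100% | 95% |
| 9 | 100% | 95% | 33% |
| 10 | 100% | 44% | 1% |

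Under M the SD hardly matters. Under L and O it decides the answer, and the Protocol does not give it.

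**3. Sensitivity of rule O at SD 8.** With a bias of 2 µm, power falls from 95% to about 58%. If a participant's two eyes were fully correlated (effective n = 82, an extreme assumption) and bias were zero, it falls to about 68%.

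**4. The paired test against ±20 µm.** The smallest significant observed mean difference is t(0.975; 162) × SD / √163, with t = 1.975:

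- SD 5: 0.8 µm
- SD 7.07: 1.1 µm
- SD 10: 1.5 µm

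With a true bias of 2 µm and SD 7.07, a test of zero difference gives p < 0.05 in about 95% of trials, while ±20 µm is met in about 100% (M), 100% (L) and 99% (O).

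**5. The 2 µm limit itself.** At SD 7.07 and zero bias, one-sided power is about 95%, as stated. If both directions must be shown at 0.025 each, it is about 90%.

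**The case against.** **The limits may be compatible.** A 2 µm limit on mean bias and ±20 µm on individual agreement could sit side by side. True, but the Protocol never says so, and the 95% would then cover only the first.

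**It may be a misprint.** Writing 2 for 20 would turn rival criteria into a slip. The arithmetic cannot exclude this (step 1). It still needs correcting, and σ would still be unstated.

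**Section 17.2 may be over-read.** A paired t-test shifted by a margin is a paired test, and two-sided 0.05 agrees with one-sided 0.025. The α figures are therefore not counted as an error here. But Section 17.2 names no margin, and a test of zero difference is the ordinary reading.

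**Some of this is SAP detail.** Whether the limits or their outer bounds are used may fairly be left to an SAP. The mismatch between Sections 6.2, 7 and 17.2 may not: an SAP could not follow all three without choosing among them or adding a link that the Protocol lacks.

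**Stronger readings that a reader might infer.** One is that the study is underpowered, from the 44%, 33% and 1% in the table. Those figures rest on SDs of 9 and 10 µm that the Protocol does not support; at 7.07 µm and zero bias every rule passes about 100% of the time. Section 3 does mention "variation of approximately 10um with repeat readings of the same eye", but this is not defined as an SD or a range and is not a between-device difference, so it does not select a row. Another inference is that σ = 5 and d = 2 were certainly used; the formula does not identify them.

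**Conclusion.** The contradiction stands on the text alone and needs no assumed SD: the stated 95% is not the power of the stated success criterion, and the analysis named for the primary endpoint, as ordinarily read, cannot support a claim of non-inferiority or equivalence. It should be fixed before the data are seen.

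Its numerical size is conditional. Power at ±20 µm is about 100% if the limit bounds the mean difference. If it bounds the limits of agreement or their outer bounds, power runs from about 100% down to 44% or 1% over assumed SDs of 7.07 to 10 µm, with independent eyes and no bias. Whether 163 eyes are too few, enough or more than enough cannot be told from the Protocol.

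**What to change.** 1. **Reconcile 2 µm with ±20 µm** in the Synopsis and Sections 6.2 and 7, correcting the 2 if it is a misprint. State one primary criterion with its comparator or comparators, limit, direction, and bounded quantity (the mean difference by its CI, the limits of agreement, or their outer confidence bounds). If 2 µm stays as a separate limit on mean bias, say that the 95% power applies only to it.
2. **State σ**, its source, and whether it is a per-device SD or an SD of paired differences.
3. **Restate the power** of the planned number for that criterion under a stated SD and bias, allowing for the correlation between a participant's two eyes, since Section 7 expects most participants to contribute both. The independent-eye, zero-bias figures above are illustrations, not replacement text.
4. **Align Section 17.2** so that the interval or limits, set against the chosen margin, decide the primary endpoint. Paired tests of zero difference can remain as descriptive support.

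The cost is rewording in four places and one recalculation. The stated power becomes conditional and may look less favourable. Whether the sample size must change will be known only once the criterion and the SD of differences are stated.

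### Section 7 counts 163 eyes as independent but draws them from 82–100 people and gives sigma no value, so the stated 95% power is not supported

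*Protocol*

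**What the plan says.** Section 7 (Sampling) of the protocol sets the sample size for a non-inferiority comparison "with the alpha error set at <0.025", "and power at 0.95" and "a non-inferiority limit of 2" µm. It arrives at 163 eyes, "which would likely mean 82 to 100 participants, assuming most are able and willing to have tests performed on both eyes". The formula is n = f(α, β) × 2 × σ² / d², with σ described only as the standard deviation. The synopsis carries 82–100 participants forward as the planned size.

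Two other places give figures that might bear on σ. Section 3 reports "variation of approximately 10um with repeat readings of the same eye" for the PM1. Section 6.2 expects about 95% of "corneal thicknesses which are measured will be within the range of 480um to 620um".

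On analysis, Section 17.2 says that "the primary endpoint will be analysed using paired tests or non-parametric equivalents". It does not mention that a person may contribute two eyes. The success criterion in Section 6.2 is stated on another scale, "using the Bland Altmen equation/approach based on +/-20micron equivalency".

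**The concern.** The lower figure of 82 is 163/2 rounded up, so each eye is counted as a full independent unit. The formula has no term for correlation between the between-device differences in a person's two eyes. If those differences are positively correlated, 163 eyes from 82–100 people carry less information than 163 independent eyes.

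The size of that loss depends on σ, which is undefined. It could be the error SD of one device within an eye, in which case the factor 2 belongs in the formula. It could be the SD of the paired differences, in which case the factor 2 is surplus and leaves a reserve. A reader cannot tell which, and so cannot tell whether the planned number of people delivers the stated power at 2 µm.

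The analysis section leaves the same gap. Paired tests run on eyes as if independent would give intervals that are too short and a one-sided error above 2.5% whenever fellow-eye differences are positively correlated.

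**Working it through.** **Inputs.** From Section 7: alpha 0.025 (taken as one-sided, the usual reading for non-inferiority), power 0.95, d = 2 µm, N = 163 eyes, 82–100 people. Assumed: a true mean difference of 0, and a fellow-eye correlation ρ of the between-device differences, shown over a range because the protocol gives none.

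**1. The plan's own figure.** f = (1.960 + 1.645)² = 12.995, so n = 12.995 × 2 × σ² / 4. With no σ, 163 cannot be computed. Solving backwards, σ = 5 gives 162.4, rounded up to 163; the figure needs σ between 4.99 and 5.01.

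**2. Do the protocol's other figures supply σ?** The same formula at d = 2 µm gives:

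| Source and reading | σ (µm) | Eyes |
|---|---|---|
| Section 6.2 range: (620 − 480)/(2 × 1.96) | 35.7 | about 8,300 |
| Section 3, 10 µm as an SD | 10 | 650 |
| Section 3, 10 µm as 1.96 SD | 5.10 | 170 |
| Section 3, 10 µm as a repeatability coefficient (2.77 SD) | 3.61 | 85 |
| Section 3, 10 µm as a full 95% width (3.92 SD) | 2.55 | 43 |

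The first is a between-eye SD and cannot be what lies behind 163. The others run from 43 to 650 because Section 3 does not say what its 10 µm measures.

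**3. Allowing for two eyes per person.** Let p people give two eyes and s give one, with N = 2p + s = 163. For 82 people, p = 81 and s = 1; for 100 people, p = 63 and s = 37. With V the variance of a paired difference,

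Var(mean difference) = V × DE / N, where DE = (2p(1 + ρ) + s) / N, and power = Φ(2/SE − 1.96).

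*Without assuming σ.* The largest V that keeps 95% power is (2/3.605)² × 163 / DE. As an SD of paired differences, in µm:

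| ρ | 0 | 0.3 | 0.5 | 0.8 |
|---|---|---|---|---|
| 82 people | 7.1 | 6.2 | 5.8 | 5.3 |
| 100 people | 7.1 | 6.4 | 6.0 | 5.6 |

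*If σ = 5 is a within-eye error SD, with errors independent between devices* (V = 2 × 25 = 50), power is:

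| ρ | 0 | 0.3 | 0.5 | 0.8 |
|---|---|---|---|---|
| 82 people | 95.1% | 88.7% | 83.9% | 76.9% |
| 100 people | 95.1% | 90.2% | 86.6% | 81.0% |

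*If σ = 5 is the SD of paired differences* (V = 25), power for 82 people is 99.9% at ρ = 0, 98.7% at ρ = 0.5 and 95.1% at ρ = 1.

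**4. If the paired tests treat eyes as independent.** Coverage of a nominal 95% interval is 2Φ(1.96/√DE) − 1, and one-sided error is 1 − Φ(1.96/√DE). Neither depends on σ.

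| | ρ | 0.3 | 0.5 | 0.8 |
|---|---|---|---|---|
| 82 people | DE | 1.298 | 1.497 | 1.795 |
| | Coverage | 91% | 89% | 86% |
| | One-sided error | 4.3% | 5.5% | 7.2% |
| 100 people | DE | 1.232 | 1.387 | 1.618 |
| | Coverage | 92% | 90% | 88% |
| | One-sided error | 3.9% | 4.8% | 6.2% |

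**5. Scale against ±20 µm.** With V = 50 and 82 people, the 95% half-width for the mean difference is 1.96 × √(50/163) = 1.09 µm if clustering is ignored, and 1.24, 1.33 and 1.45 µm at ρ = 0.3, 0.5 and 0.8 when it is allowed for.

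**The case against.** The strongest reply is that this hardly touches the only stated success criterion. Section 6.2 judges agreement against ±20 µm, and the 2 µm limit appears only in Section 7. Against 20 µm, even a half-width of 1.45 µm is immaterial. That stands, and it confines the concern to the 2 µm power statement and to the validity of the intervals. It does not rescue Section 7, which justifies the sample size on 2 µm. That the two limits conflict is a separate matter.

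Secondly, the power loss may not exist. If σ is the SD of paired differences, a natural reading in a within-eye design, power is at least 95% at every ρ. Even starting from V = 50, a positive same-eye correlation r between devices reduces the variance to 50(1 − r), and 82 people keep 95% power once r reaches 0.23, 0.33 or 0.44 at ρ = 0.3, 0.5 or 0.8. This also stands, and is why the conclusion is that power is unsupported rather than too low.

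Thirdly, handling of two eyes may be set out in a statistical analysis plan, and paired tests on participant means would fit the wording of Section 17.2. The coverage and error figures are therefore conditional on eyes being analysed as independent. But Section 7 itself counts eyes that way, and Section 17.2 names a simple paired test without qualification, so the protocol points towards that analysis.

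Lastly, the documents elsewhere refer to a single study eye (Sections 8, 12 and 15.1). With one eye per person the clustering disappears, but 82–100 people would then fall short of 163 eyes. That inconsistency needs settling, and does not answer this point.

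**Conclusion.** The concern holds. Section 7 treats 163 eyes as independent while taking most of them in pairs from 82–100 people, and the one input needed to check the figure is missing. On one reading of σ, power for 82 people falls to 77% at ρ = 0.8; on another it never drops below 95%. That spread is the reason the 95% claim cannot be accepted as written. The arithmetic of 163 is not shown to be wrong, since an unreported σ of about 5 µm returns it.

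The figures rest on a one-sided alpha of 0.025, a true mean difference of zero, an assumed ρ and, where stated, the back-solved σ. At ρ = 0 nothing is lost. The error inflation applies only if eyes are analysed as independent. The point should be corrected before analysis; its consequences lie at the 2 µm limit and are minor at ±20 µm.

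**What to change.** 1. **Section 7.** State the value and source of σ and say what it is the SD of. If it is the SD of paired differences, remove the factor 2. Restate the power of 163 eyes from 82 and from 100 people over a stated range of ρ.
2. **Section 17.2.** Replace the simple paired test on eyes with an analysis that accounts for two eyes per participant, such as a participant random effect or a participant-clustered bootstrap, for both the mean differences and the limits of agreement.

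The cost is wording in two sections and a mixed model or clustered bootstrap in place of a paired test. The restated power may be less favourable and the intervals slightly wider. No extra participants are asked for.
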